# FAQLQ-PF

## Food Allergy Quality of Life Questionnaire – Parent Form (0-12 years)

**To cite this questionnaire:**

**Food Allergy Quality of Life Questionnaire-Parent Form  
(FAQoL-PF)  
Children aged 0-12 years**

**Instructions to Parents**

- The following are scenarios that parents have told us affect children's quality of life because of food allergy.
- Please indicate how much of an impact each scenario has on **your child's quality of life** by placing a tick or an x in one of the boxes numbered 0-6.

**Response Options**

0 = not at all  
1 = a little bit  
2 = slightly  
3 = moderately  
4 = quite a bit  
5 = very much  
6 = extremely

**All information given is completely confidential.  
This questionnaire will only be identified by a code number.**

- If your child is aged 0 to 3 years, please answer Section A.
- If your child is aged 4 to 6 years, please answer Section A & Section B.
- If your child is aged 7 years and over, please answer Section A, Section B & Section C.

**SECTION A**

Not at all Extremely  
→

Because of food allergy, my child feels.....		0	1	2	3	4	5	6
1	Anxious about food							
2	Different from other children							
3	Frustrated by dietary restrictions							
4	Afraid to try unfamiliar foods							
5	Concerned that I am worried that he/she will have a reaction to food							

Not at all Extremely  
→

Because of food allergy, my child.....		0	1	2	3	4	5	6
6	Experiences physical distress							
7	Experiences emotional distress							
8	Has a lack of variety in his/her diet							

Not at all Extremely  
→

Because of food allergy, my child has been negatively affected by.....		0	1	2	3	4	5	6
9	Receiving more attention more attention than other children of his/her age							
10	Having to grow up more quickly than other children of his/her age							
11	His/her environment being more restricted than other children of his/her age							

Not at all Extremely  
→

Because of food allergy, my child's social environment is restricted because of limitations on.....		0	1	2	3	4	5	6
12	Restaurants we can safely go to as a family							
13	Holiday destinations we can safely go to as a family							

Not at all Extremely  
→

Because of food allergy, my child's ability to take part has been limited.....		0	1	2	3	4	5	6
14	In social activities in other people's houses ( sleepovers, parties, playtime )							

- If your child is aged 0 to 3 years, please now go to Section D.
- If your child is aged 4 to 12 years, please now answer Section B.

**SECTION B**

Not at all Extremely  
—————→

Because of food allergy, my child's ability to take part has been limited.....		0	1	2	3	4	5	6
15	In preschool/school events involving food ( class parties/treats/lunchtime )							

Not at all Extremely  
—————→

Because of food allergy, my child feels.....		0	1	2	3	4	5	6
16	Anxious when going to new places							
17	Concerned that he/she must always be cautious about food							
18	'Left out' in activities involving food							
19	Upset that family social outings ( eating out, celebrations, days out ) have been limited by food allergy							
20	Anxious about accidentally eating an ingredient to which he/she is allergic							
21	Anxious when eating with unfamiliar adults/children							
22	Frustrated by social restrictions							

Not at all Extremely  
—————→

Because of food allergy, my child.....		0	1	2	3	4	5	6
23	Is more anxious in general than other children of his/her age							
24	Is more cautious in general than other children of his/her age							
25	Is not as confident as other children of his/her age in social situations							
26	Wishes his/her food allergy would go away							

- If your child is aged **6 years and under**, please now go to **Section D**.
- If your child is aged **7 years and older**, please answer **Section C**.

Not at all Extremely  
—————→

**SECTION C**

Because of food allergy, my child feels.....		0	1	2	3	4	5	6
27	Worried about his/her future (opportunities, relationships)							
28	That many people do not understand the serious nature of food allergy							
29	Concerned by poor labelling on food products							
30	That food allergy limits his/her life in general							

**SECTION D.**

Please answer the following questions with reference to the 6-point scale on the right

- |                        |
|------------------------|
| 0 = extremely unlikely |
| 1 = very unlikely      |
| 2 = somewhat unlikely  |
| 3 = likely             |
| 4 = quite likely       |
| 5 = very likely        |
| 6 = extremely likely   |

**Q1. What chance do you think your child has of ....?**

	Question	6-point Scale						
		0	1	2	3	4	5	6
1	.....accidentally ingesting the food to which they are allergic ?							
2	.....having a severe reaction if food is accidentally ingested ?							
3	.....dying from his/her food allergy following ingestion in the future ?							
4	.....effectively treating him/herself, or receiving effective treatment from others (including EpiPen administration), if he/she accidentally ingests a food to which he/she is allergic ?							

[figure not shown]
**Q2. What chance does your child think he/she has of .....?**

	Question	6-point Scale						
		0	1	2	3	4	5	6
1	.....accidentally ingesting the food to which they are allergic ?							
2	.....having a severe reaction if food is accidentally ingested ?							
3	.....dying from his/her food allergy following ingestion in the future ?							
4	.....effectively treating him/herself, or receiving effective treatment from others (including EpiPen administration), if he/she accidentally ingests a food to which he/she is allergic ?							

## APPENDIX 8 SCORAD

SCORAD EUROPEAN TASK FORCE ON ATOPIC DERMATITIS		INSTITUTION	
Last Name  First Name 		PHYSICIAN	
Date of Birth:  DD/MM/YY	Topical Steroid used: Potency (brand name) 		
Date of Visit: 	Amount / Month  (G)		
			Number of flares / Month 

[figure not shown]

4.5 (8.5)

4.5 18 4.5

1 1

(6) 9 9 (6)

4.5 (8.5)

4.5 18 4.5

1 1

(6) 9 9 (6)

Figures in parenthesis  
for children under two years

A: EXTENT Please indicate the area involved 	
B: INTENSITY 	C: SUBJECTIVE SYMPTOMS PRURITUS+SLEEP LOSS 

CRITERIA	INTENSITY	MEANS OF CALCULATION	
Erythema/darkening		INTENSITY ITEMS (average representative area) 0= absence 1= mild 2= moderate 3= severe * Dryness is evaluated on uninvolved areas	Objective SCORAD A/5+7B/2  /83
Edema/papulation			
Oozing/crust			
Excoriation			
Lichenification/prurigo			
Dryness*			SCORAD A/5+7B/2+C  /103

Visual analog scale (average for the last 3 days or nights)	PRURITUS (0 to 10) 	
	SLEEP LOSS (0 to 10) 	0 10

TREATMENT:

REMARKS:

10

Source: Kunz B, Oranje AP, Labrèze L, Stalder JF, Ring J, Taïeb A. Clinical validation and guidelines for the SCORAD index: consensus report of the European Task Force on Atopic Dermatitis. *Dermatology*. 1997;195(1):10-9.

## LIST OF ABBREVIATIONS

AE / AESI	Adverse event / Adverse event of special interest
ANCOVA	Analysis of covariance
ATC	Anatomical Therapeutic Chemical (Classification System)
BOCF	Baseline Observation Carried Forward
BSA	Body Surface Area
CI	Confidence interval
CTCAE	Common Terminology Criteria for Adverse Events
CTMS	Clinical trials Management System
D	Day
DBPCFC	Double-blind, placebo-controlled food challenge
DSMB	Data and Safety Monitoring Board
eCRF	Electronic case report form
ED	Eliciting Dose
EPIT	EPicutaneous ImmunoTherapy
ET	Early Termination
FAQLQ	Food Allergy Quality of Life Questionnaire
FAIM	Food Allergy Independent Measure
FAS	Full analysis set
FEV 1	Forced expiratory volume in one second
ICF	Informed consent form
IgE, IgG, IgG4	Immunoglobulin E, immunoglobulin G, immunoglobulin G4 subtype
IQR	Interquartile range
IP	Investigational product
ITT	Intent-to-treat
IWRS	Interactive Web Response System
M	Month
mBOCF	Modified BOCF
MedDRA	Medical Dictionary for Regulatory Activities
PC	Phone Contact
PEF	Peak Expiratory Flow

PP	Per-protocol
PT	Preferred term
PDV	Protocol deviation
Q1, Q3	First, third quartile
SAE	Serious adverse event
SAP	Statistical analysis plan
SCORAD	Scoring atopic dermatitis
SE	Standard Error
SOC	System organ class
SPT	Skin prick test
TEAE	Treatment-emergent adverse event
TFL	Tables, Figures and listings
US(A)	United States (of America)
UV	Unscheduled visit
V	Visit
WHO	World Health Organization

## 1 INTRODUCTION

This Statistical Analysis Plan (SAP) describes the statistical methods to be used for the reporting and analyses of data collected under the DBV Technologies Phase III protocol PEPITES.

This SAP is based upon the following study documents:

- Study Protocol, Version Final (July 20, 2015),
- Amended protocol, Version 2.0 (December 9, 2015)
- Electronic Case Report Form (eCRF), Version 4.0 (June 23, 2016)
- CCI [REDACTED]
- SDTM annotated CRF, Version 1.3 (October 07, 2016)
- SDTM Data Transfer Mapping Specifications, Version 1.3 (January 17, 2017)

## 2 STUDY OBJECTIVES

The objective of this study is to assess the efficacy and the safety of Viaskin® Peanut to induce desensitization to peanut in peanut-allergic subjects 4 through 11 years of age after a 12-month treatment period by EPIT (Epicutaneous immunotherapy).

## 3 INVESTIGATIONAL PLAN

### 3.1 Overall Study Design and Plan

This is a 12-month, Phase III, double-blind, placebo-controlled, randomized study to assess the efficacy and safety of Viaskin® Peanut, dosed at 250 µg peanut protein (per patch) in peanut-allergic children from 4 through 11 years of age.

The overall maximum study duration for each subject is approximately 61 weeks (6-week screening period, 12-month treatment period and 2-week follow-up period).

During the maximum 6-week screening period, subjects will undergo a first screening visit and an entry double-blind, placebo-controlled food challenge (DBPCFC) to peanut to confirm their allergy and their entry peanut eliciting dose (ED). The starting dose of the challenge will be 1 mg peanut protein and will escalate up to a highest dose of 300 mg peanut protein. Subjects who react at or below the dose of 300 mg peanut protein are considered eligible. Randomization of eligible subjects will occur in a 2:1 ratio to Viaskin® Peanut dosed at 250 µg peanut protein (active treatment) or placebo. Subjects will be stratified at randomization by their entry/screening DBPCFC ED in one of the following two strata:

---

 PEPITES: A Double-blind, Placebo-controlled, Randomized Phase III Pivotal Trial to Assess the Efficacy and Safety of Peanut Epicutaneous Immunotherapy with Viaskin® Peanut in Peanut-allergic Children

- Stratum 1: children with a screening ED of 1 mg, 3 mg or 10 mg;
- Stratum 2: children with a screening ED of 30 mg, 100 mg or 300 mg.

The randomization scheme will ensure that the ratio of active treatment to placebo is maintained in each stratum.

Subjects randomized in the study and consenting for the genetic analysis on a voluntary basis will be assessed for mutations in the filaggrin gene. Subjects' participation for this genetic analysis will be optional.

Subjects will apply a Viaskin® patch containing either peanut protein or placebo daily for a period of 12 months. At Month 12, a second DBPCFC to peanut will be performed, with a starting dose of 1 mg peanut protein with escalation up to a highest dose of 2,000 mg peanut protein. This evaluation will help determine the primary efficacy endpoint of this pivotal study.

Subjects will undergo other efficacy parameter assessments at Months 3, 6 and 12, including immunological changes in peanut-specific immunoglobulin E (IgE), peanut-specific immunoglobulin G4 (IgG4) and skin prick tests (SPTs).

Key assessments of global safety will be performed at each study visit by the Investigators, including skin observation of the patch areas of application (inter-scapular area of the back), spirometry, peak expiratory flow (PEF) measurements, vital signs, physical examinations and clinical laboratory assessments. Atopic dermatitis will also be assessed at Baseline and at Months 3, 6 and 12 using the SCORAD (Scoring atopic dermatitis), for which specific training will be provided for better use and accurate assessment.

In between visits, the severity of local skin reactions will be assessed on a daily basis by the subjects (parents/guardians) in their diary for 6 months. Any other adverse events (AEs), local skin reactions occurring after the first 6 months of treatment and any concomitant medications will also be reported in the diary by the subjects and this will be reviewed by the site medical staff at each patient visit. The 3 pre-specified solicited symptoms graded daily by the subjects in their diaries, itching, redness and swelling at the patch skin location, will not be reported by the Investigators in the adverse events form of the e-CRF, except if these symptoms are part of another concomitant disease or if they result in the subject's study discontinuation or consider as a serious adverse event.

[figure not shown]
In addition, the adhesion of the patch to the skin, especially the maintenance of the occlusion of the patch, will be assessed by the subjects' parents/guardians for 28 days of treatment (whenever possible, these should be consecutive days). This assessment will be conducted during a period between Month 3 and Month 9. On the same days, photographs of the patches attached to the skin will be made by the subjects' parents/guardians as instructed. The review of these photos will allow the Investigators to control and ensure that the parents' assessments of the patch adhesion were satisfactory. The trained site staff will also assess the patch adhesion of all subjects at each subject visit (without removing the patch).

After completion of the PEPITES study, all eligible subjects, including the placebo subjects, will be offered the opportunity to participate in an open-label extension study (PEOPLE) to receive Viaskin® Peanut 250 µg for 24 additional months of treatment. Subjects who will decide to roll-over into the extension study will have their last PEPITES study visit at Visit 11 and they will start the extension study at that visit. Subjects who decide not to roll-over into the extension study will continue their visit schedule up to Visit 12.

The study will be conducted at approximately 28 to 40 centers in 4 to 7 countries in Australia, Europe and North America with Investigators and staff who are trained and experienced in the diagnosis and management of peanut allergy and anaphylaxis, and equipped and capable of performing a DBPCFC in children.

The study design is presented below in Figure 1.

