#### 6.2.1.4 Recording Adverse Events

Adverse event reporting will start at the signature of the informed consent form (ICF) and end after the 2-week follow-up period (End of Study V12 Visit). During the screening period (that is, from the time of ICF signature through Day-1), only SAEs will be recorded in the e-CRF; during the screening period, AEs that do not meet any seriousness criteria will be documented in the subject's source documents. Adverse events occurring after the end of the study should be reported to the Sponsor by the Investigator if the Investigator considers that there is a causal relationship with the study drug.

Adverse events still ongoing at the time of the End of Study Visit will be followed up for an additional 30 days, or until they resolve or stabilize, whichever comes first.

All AEs occurring on or after the day of the first dose of study drug, regardless of the relationship to the study drug, will be recorded in the e-CRF.

All AE reports in the e-CRF should contain the following information of the event: date and time of onset, date and time of resolution, severity, treatment required, relationship to study drug, action taken with the study drug, outcome, and whether the event is classified as serious or not.

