#### 4.9.1 Adverse Events

Treatment-emergent AEs will be defined as any AEs, regardless of relationship to study drug reported during or after the initial Viaskin® patch application, i.e.:

- New event, or
- Condition already present that worsens in either severity or relationship to study drug following exposure to Viaskin® patches.

AEs occurring after the end of the study (Visit 11 or Visit 12) will be recorded only if the investigator considers that there is a causal relationship with the study drug and as such, will be considered also as TEAEs.

Pre-treatment emergent AE will be defined as an AE that begins before the first administration of study drug and that does not worsen in severity after the first administration of study drug. During the screening period (from the ICF signature to Day-1), only SAEs are recorded in the database (AEs are only documented in the source documents).

Where dates are missing or partially missing, adverse events will be assumed to be treatment-emergent, unless there is clear evidence (through comparison of partial dates) to suggest that the adverse event started prior to the first dose of study treatment.

More specifically:

- Start date of AE missing: Assumed to be date of first treatment dose.
- Start day and month of AE missing: Assumed to be date of first treatment dose (if same year for both dates), January 1st otherwise.
- Start day of AE missing: Assumed to be date of first treatment dose (if same month and year for both dates), first day of the month otherwise.
- End date for non-ongoing AE missing: Assumed to date of last treatment dose
- End day and month for non-ongoing AE missing: Assumed to be date of last treatment dose (if same year for both dates), December 31st otherwise.

- End day for non-ongoing AE missing: Assumed to be date of last treatment dose (if same month and year for both dates), last day of the month otherwise.

TEAEs with missing severity will be considered as “severe”; TEAEs with missing relationship to the study drug will be considered as “drug-related”.

TEAEs reported as related, probably related, or possibly related to the study drug will be considered as related to IP.

Viaskin Peanut-induced Local TEAEs are defined as TEAEs considered as related to IP with a High Level Term equal to “Application and instillation site reactions” and will be flagged in the analysis datasets.

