For each summary presented by SOC and PT, the SOC “General disorders and administration site conditions” will be tabulated globally as well as split in 2 subsections:

- General disorders (High Level Term not equal to “Application and instillation site reactions”),
- Administration site conditions (High Level Term equal to “Application and instillation site reactions”).

All AEs will be coded using the latest available version of the MedDRA dictionary.

Symptoms related to DBPCFC are reported in tables separately from other AEs.

AEs related to accidental peanut consumption are reported with other AEs.

An overall overview table of AEs (to be distinguished from symptoms/reactions elicited during the DBPCFCs) will be provided showing the number of subjects, the percentage of subjects and the number of events, overall and for each treatment group, for the following categories of AEs:

- Any AE,
- Any serious AEs,
- AEs leading to study treatment discontinuation,
- AEs leading to death,
- Any mild AEs,
- Any moderate AEs,
- Any severe AEs.

Additionally, an overall overview table of TEAEs will be provided showing the number of subjects, the percentage of subjects and the number of events for the following categories of TEAEs:

- Any TEAE,
- Any serious TEAEs,
- Any TEAEs considered related to IP:
  - ┆ Any TEAE reported as related,
  - ┆ Any TEAE reported as probably related,
  - ┆ Any TEAE reported as possibly related,
- Any TEAEs considered unrelated to IP:
  - ┆ Any TEAE reported as unlikely related,
  - ┆ Any TEAE reported as unrelated,
- Any Serious TEAEs considered related to investigational product (IP),
- Any TEAEs leading to permanent study treatment discontinuation,
- Any TEAEs leading to temporary study treatment discontinuation,
- Any TEAEs leading to death,

- Any mild TEAEs,
- Any moderate TEAEs,
- Any severe TEAEs,
- Any severe TEAEs considered related to IP (reported as related, probably or possibly related),
- Any Viaskin Peanut-induced Local TEAE,
- Any severe Viaskin Peanut-induced Local TEAE,
- Any systemic allergic TEAE considered related to IP (reported as related, probably or possibly related)
- Any TEAE leading to an epinephrine intake
  - ⌞ Considered related to IP
  - ⌞ Considered unrelated to IP.

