- By maximum severity (severe, moderate and mild): Subjects will be counted once per SOC and once per PT at the worst severity. If the severity is missing, the worst severity will be assumed.
- By maximum duration. For these tables TEAEs will be presented by SOC, PT within each SOC and maximum duration within each PT (using the classes for duration in days: 1-7, 8-15, 16-30, 31-60, 61-90, above 91). For AEs ongoing at the end of the study, duration will be imputed based on the date of subject end of study. For AEs not ongoing but with missing end date, duration will be imputed based on date of last study treatment.

Additionally, for TEAEs and TEAEs considered related to IP, tables showing number of subjects, percentage of subjects and number of events by severity will be provided. Subjects will be counted once per SOC, per PT and per severity. For these specific tables, if the severity is missing, no hypothesis will be assumed to replace the missing severity.

Adverse event summaries will be ordered in terms of decreasing frequency for SOC, and PT within SOC, in the Viaskin® treatment group, and then similarly by decreasing frequency in the placebo group, and then alphabetically for SOC, and PT within SOC.

The proportions of patches during the one-year exposure period that led to mild, moderate or severe TEAE considered related to IP will be summarized on the Safety population (overall, by screening ED subgroup and by class of age). For this analysis, the worst ongoing severity will be considered for each day of exposure and the following definitions will be used:

- % of patches leading to severe TEAE will be estimated as =

$$100 \left( \frac{\text{Number of days with ongoing severe TEAE}}{\text{Exposure duration}} \right)$$

- % of patches leading to moderate TEAE will be estimated as =

$$100 \left( \frac{\text{Number of days with ongoing moderate (1) TEAE}}{\text{Exposure duration}} \right)$$

(1) without concomitant event of severe intensity

- % of patches leading to mild TEAE will be estimated as =

$$100 \left( \frac{\text{Number of days with ongoing mild (2) TEAE}}{\text{Exposure duration}} \right)$$

(2) without concomitant event of moderate or severe intensity

The proportion of patches during the one-year exposure period that led to Viaskin® Peanut 250 µg-induced AEs will also be summarized the same way as above.

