#### 4.9.3 Local skin reactions as collected in the diary

Number and percentage of subjects with evaluable diary data will be presented.

Local skin reactions at sites of Viaskin® application as assessed by the patient and documented in the diary during the first 6 months of the study treatment will be summarized for itching, redness, swelling, and any local reaction (itching, redness and swelling) using:

- The number and percentage of subjects by maximum severity grade reported (1, 2 or 3) among subjects with evaluable diary data and among subjects with a reaction (grade  $\geq 1$ )
- The number and proportion of days with a reaction reported (based on days with patches graded by type of reaction or for at least one reaction between itching, redness and swelling when reported on any local reaction) among subjects diary data,
- The proportion of days scored by severity grade (worst severity grade per day is considered).

All proportions will be calculated as

$$\left( \frac{\text{Number of days with a reaction reported}}{\text{Number of days with patches graded}} \right)$$

Proportion of days with no assessment of local skin reaction out the number of patches entered in the diary will be provided.

The number of days with a reaction reported and number of days with patches graded will be calculated based on removal dates.

The periods considered for the reporting will be:

- r The overall first 6 months (D1 to D180),
- r Month 1 (D1 to D30),
- r Month 2 (D31 to D60),
- r Month 3 (D61 to D90),
- r Month 4 (D91 to D120),
- r Month 5 (D121 to D150),
- r Month 6 (D151 to D180)

The above analysis will be repeated for subjects with filaggrin gene mutations versus wild type subjects.

All local skin reactions reported by the subject will be listed.

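### The local-TEAE rows and one-year patch percentages in SAP 4.9.1 omit most diary-solicited itching, redness and swelling for Days 1–180, and nothing in their labels says so

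*SAP*

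**What the plan says.** **Recording rule.** SAP 3.1 says that the three solicited symptoms at the patch site "will not be reported by the Investigators in the adverse events form of the e-CRF". There are three exceptions: "except if these symptoms are part of another concomitant disease or if they result in" study discontinuation, or if they count as serious. The same section says that the severity of local reactions "will be assessed on a daily basis by the subjects (parents/guardians) in their diary for 6 months".

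**Outputs built on TEAEs.** In SAP 4.9.1, "Viaskin Peanut-induced Local TEAEs are defined as TEAEs considered as related to IP with a High Level Term equal to" the application-site term. The overview table has a row for any such event and a row for "Any severe Viaskin Peanut-induced Local TEAE". The section also summarizes "The proportions of patches during the one-year exposure period that led to mild, moderate or severe TEAE considered related to IP", and repeats the measure for product-induced AEs. Each percentage is the number of days with an ongoing TEAE of the given severity, divided by exposure duration. SAP 4.7 defines that duration as last patch date minus first patch date plus 1, ignoring interruptions.

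**Separate outputs.** Under SAP 4.9.3, reactions "documented in the diary during the first 6 months of the study treatment will be summarized" by maximum grade per subject, by number and proportion of days, and by grade, for Days 1–180 overall and month by month. SAP 4.9.4 tabulates investigator grades by visit and the worst grade over treatment.

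**Protocol.** Section 6.2.1.4 requires that "All AEs occurring on or after the day of the first dose of study drug, regardless of the relationship to the study drug" be recorded in the e-CRF. SAP 4.13 lists the days-with-TEAE description as an addition to the protocol, but does not list the recording rule of SAP 3.1.

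**The concern.** The recording rule removes the commonest expected patch reactions from the data source that SAP 4.9.1 then uses. The percentage is labelled as covering a year of exposure and its denominator does cover the year. For about half of that time its numerator is closed to ordinary itching, redness and swelling. The result is neither a one-year measure of local reactions nor a measure of the remaining events over a stated period. It joins two recording rules over one denominator.

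Protocol 1.3 names local reactions as the expected effect of the patch. A reader who takes local burden from the TEAE overview or the patch-percentage table will get a figure lower than the diary supports. The comparison between arms in those tables is likely to be reduced as well.

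**Working it through.** The plan states no figure here to reproduce. The check follows the data and then applies the SAP's own formula.

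**1. Data flow.** A local TEAE must be a TEAE record with a coded High Level Term. A solicited symptom outside the three exceptions creates no such record. Diary grades are not an input to any SAP 4.9.1 output, and that section carries no caveat.

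**2. Share of the denominator.** Assume 365 days of exposure.
- Days 1–180: 180/365 = 49.3%.
- Remaining days: 185/365 = 50.7%.

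**3. A limiting case.** Take a child who has only solicited symptoms, every day, with no exception met. The true proportion of days is 100%.
- If the exclusion ends at Day 180, the SAP formula gives at most 185/365 = 50.7%.
- If it runs to Month 12, the formula gives 0/365 = 0%. The SAP 4.9.3 tables, which stop at Day 180, would not show Months 7–12 either.

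The SAP does not say which applies. The rule refers to symptoms graded daily, and daily grading lasts 6 months, so the first reading is the natural one.

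**4. Illustrative size.** Protocol Table 5 gives the mean percentage of the first 90 days with each diary grade in VIPES children on 250 µg (N=28). Points of a 365-day percentage = rate × days / 365. For grade 2–3 redness: 25.6 × 90 / 365 = 6.3, that is 0.256 × 90 = 23.0 days.

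| Diary symptom | Rate (%) | 90 days | 180 days |
|---|---|---|---|
| Redness, grade 2–3 | 25.6 | 6.3 | 12.6 |
| Itching, grade 2–3 | 22.1 | 5.4 | 10.9 |
| Swelling, grade 2–3 | 20.8 | 5.1 | 10.3 |
| Itching, grade 3 | 5.9 | 1.5 | 2.9 |
| Swelling, grade 3 | 5.9 | 1.5 | 2.9 |
| Redness, grade 3 | 4.1 | 1.0 | 2.0 |

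The last column assumes that the 90-day rate continues to Day 180. The rows must not be added, because symptoms share days. They show the diary days at issue and not an exact shortfall, because another event on the AE form may cover some of the same days.

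**5. Direction.** The rule applies to both arms. In VIPES, local reactions occurred in more than 90% of subjects on active patches and in 50% on placebo (Protocol 1.1.1.2.3). If a similar gap holds here, more events are dropped from the active arm and the difference shrinks.

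**6. Other outputs from the same source.** The exceptions cover study discontinuation but not a temporary stop. The table of TEAEs leading to temporary discontinuation therefore misses solicited symptoms that caused one. The table of TEAEs leading to topical corticosteroid use needs an AE-form entry linked to the medication, so a treated solicited symptom has nothing to link to.

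**The case against.** The strongest reply is that these symptoms are not lost. SAP 4.9.3 reports them from the diary for exactly Days 1–180, SAP 4.9.4 adds investigator grades, and SAP 4.9 runs the safety analysis by arm, age range and screening ED subgroup. Protocol 3.2.2 and 8.6.1 also treat subject-assessed local tolerance as a separate item. That stands. A reader might infer that local harm as a whole is understated for the first 6 months, and the documents do not support this.

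Three further limits also stand.
- It is tempting to use the 241 of 343 related TEAEs (70.3%) that began before Day 180 in VIPES children (Protocol Table 4) as the share omitted. That table counts related TEAEs of every kind, and the protocol does not say that VIPES used this recording rule. Nor can one say that nearly all diary days would score zero, because papules, dermatitis, vesicles and grade 4 reactions still reach the AE form.
- Diary grade is not AE severity, which Protocol 6.2.1.3.2 judges by interference with general condition. For VIPES children on 250 µg, Protocol 1.1.1.2.6 says local reactions may be severe on 1 day or more in about 35%. Table 5 shows a severe related TEAE in the general and administration-site class in 1 of 28 (3.6%). The two scales should not be merged.
- Protocol 6.2.1.4 speaks of the e-CRF and not of one form within it, so the conflict is less than absolute. However, where the protocol wants reactions kept off the AE pages it says so, as section 6.2.1.3.6 does for food-challenge symptoms. It makes no such statement for patch-site symptoms.

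The separate tables do not change what the SAP 4.9.1 figures are labelled as measuring.

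**Conclusion.** The point holds for the TEAE-based outputs of SAP 4.9.1: the local and severe-local TEAE rows, both one-year patch percentages, and the temporary-discontinuation and topical-corticosteroid TEAE tables. Followed as written, these omit most solicited itching, redness and swelling for Days 1–180, about 49% of a 365-day denominator, without a caveat or an entry in SAP 4.13.

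The diary days at issue come to about 5 to 13 percentage points for a grade 2–3 symptom and 1 to 3 points for grade 3. That rests on VIPES rates from 28 children, 365 days of exposure and, at the upper end, the 90-day rate lasting 180 days. A smaller active–placebo contrast in these tables is likely but not certain. Efficacy conclusions, the diary tables and the investigator-grade tables are unaffected.

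**What to change.** 1. Report both patch percentages in SAP 4.9.1 separately for Days 1–180 and after Day 180, each over its own exposure days.
2. For Days 1–180, show beside them the diary proportion of days with a reaction, by diary grade. Do not convert it to mild, moderate or severe.
3. Label the local and severe-local TEAE rows as excluding solicited diary symptoms. Add companion rows by maximum diary grade from SAP 4.9.3. Put the same note on the temporary-discontinuation and topical-corticosteroid tables.
4. State in SAP 3.1 that the exclusion ends when daily grading ends at Month 6, so that later itching, redness and swelling are captured as AEs. Confirm that sites recorded them that way.
5. List the exclusion in SAP 4.13 as a departure from Protocol 6.2.1.4.

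The Day 1–180 data are already collected, so the cost is SAP wording and a few extra safety tables. The local-reaction figures will look less favourable.
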